**Title**

Hemodynamic effects of blood flow variation in continuous renal replacement therapy

Complete Sections 1 - 16. In sections that allow reference to sponsor protocol or grant, clearly state section and page numbers. Any information that is different or specific to the local site should be in the SLU application. Specify N/A as appropriate.

**1. Background**

Page numbers from a sponsor's protocol/grant may be referenced in 1a and 1b.

a) Provide an introduction and background information. Describe past experimental and/or clinical findings leading to the formulation of the study, if applicable. Investigator Initiated studies must cite references in the response provided or attach a bibliography. \*?HELP?\*

Critically ill patients in the intensive care unit (ICU) with renal failure requiring renal replacement therapy (RRT) are frequently started on continuous renal replacement therapy (CRRT) as the renal replacement modality of choice. At Saint. Louis University Hospital (SLUH), CRRT is provided using the NxStage System One device, which is FDA-approved for this indication. The dialysis cartridge used at SLUH is approved for blood flow rates (BFR) ranging from 50 to 600 ml / minute for CRRT, and the choice of blood flow is determined by the prescribing physician. Lower BFRs in a CRRT circuit has been linked to the frequency of clotting of the CRRT circuit in some (Dunn 2014) but not all (Castillo 2008, Prasad 2000) studies. Importantly, in the prior studies that did not show a benefit of increasing blood flow rate, most patients received anticoagulation with CRRT. However, many patients are not candidates for anticoagulation due to coagulopathy or bleeding. In these patients, if BFR can be safely increased, CRRT circuit clotting leading to interruptions of therapy might be avoided. There is paucity of data to guide adjusting BFR on CRRT and the clinical impacts of such adjustments.

Please save frequently

b) Describe any animal experimentation and findings leading to the formulation of the study, if there is no supporting human data.

NA

**2. Purpose of the study**

a) Provide a brief lay summary of the project in <200 words. The lay summary should be readily understandable to the general public.

**Protocol Title:** Hemodynamic effects of blood flow variation in continuous renal replacement therapy

Continuous renal replacement therapy (CRRT) is often prescribed as a supportive therapy in patients with renal failure in the intensive care unit. At Saint Louis University Hospital, the NxStage System One dialysis machine, along with the Nxstage Cartridge Express dialysis cartridge, is used for CRRT. Blood flow rate (BFR) is a parameter on a CRRT machine that has a range of acceptable values, and is determined by the prescribing physician. The purpose of this study is to study effects of changing blood flow from 150ml per minute to 350ml per minute in continuous dialysis on patients' hemodynamic parameters.

Page numbers from a sponsor's protocol/grant may be referenced in 2b and 2c.

**b) List your research objectives (specific aims & hypotheses of the study).**

Hypothesis:

We hypothesize that within the range of BFR currently used, and at a fixed dialysate flow rate, the impact of BFR in the CRRT machine on patient's hemodynamics will be clinically insignificant, as defined as a change in systolic blood pressure of less than 6mm mercury (see section 3d).

Specific Aims:

The goal of the study is to estimate the change hemodynamic parameters that occurs (if any) when blood flow is varied in the range specified above.

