Procedure: An attending or fellow physician who is a member of the investigator team will supervise the entire protocol at the bedside. An ICU nurse will be present during the protocol. The study physician will ensure that patient's MAP is  $\geq 65$  mm Hg prior to initiating protocol. The study protocol is divided into three periods, each lasting 10 minutes. During all three periods, dialysate flow rate will be as prescribed by the nephrology consult attending physician, and fluid removal will be set to minimal.

The pre-specified protocol BFR rates of 150 and 350 ml/min were chosen because these are values at the lower and higher end of standard of care, respectively, and the range outside of which circuit lifespan observational studies suggest circuit lifespan may decrease (Dunn 2014). The protocol consists of two separate periods of BFR set to 150 in order to account for the influence of time on hemodynamics, separate from the influence of BFR. To clarify, if hemodynamics change from period 1 to period 2, it will not be clear if this is due to change in blood flow or changes over time. Repeating measurements at low blood flow will permit estimation of time-dependent effects. Large randomized trials involving the use of CRRT have used blood flows similar to those being studied in this protocol (Vinsonneau 2006, Palevsky 2008).

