## Protocol Title:

Hemodynamic effects of blood flow variation in continuous renal replacement therapy

Hemodynamic data: blood pressure, heart rate, and vasopressor dose will be documented. If the patient's primary care team has prescribed a device for cardiac output monitoring, stroke volume will also be documented.

Period 1: CRRT will be administered with blood flow rate (BFR) of 150 ml per minute. Hemodynamic data will be documented every minute for 10 minutes

Period 2: BFR will be increased to 350 ml per minute. Hemodynamic data will be documented every minute for 10 minutes.

Period 3: BFR will be decreased back to 150 ml per minute. Hemodynamic data will be documented every minute for 10 minutes.

Blood flow rate changes will be made at approximately one minute intervals in increments of no more than 75 mL/min.

After the third study period, patients will be monitored with the ICU nurse at the bedside and the attending physician immediately available for additional 10 minutes.

After the completion of all three study periods, BFR will be returned to the level prescribed by the clinical nephrology team caring for the patient, determined by standard of care.

c) If the proposed study is a clinical trial where a drug, vaccine, device or other treatment is compared to a placebo group or comparison treatment group, what are the guidelines or endpoints by which early decisions regarding efficacy or lack of efficacy can be made? For example, it may be reasonable to stop enrollment on a study when efficacy has already been clearly demonstrated, to avoid unnecessary enrollments of additional subjects. Alternatively, it may be reasonable to stop enrollment when it is clear that efficacy will never be demonstrated, given the statistical power of the study as designed. Describe the guidelines that are in place to assist in making these determinations, if relevant to the proposed study.

NA

d) Describe how data analysis will be performed (statistical tests, methods of evaluating data) and indicate the smallest group/unit for which separate reporting will occur. For studies involving a questionnaire, if data and reliability information are available, please describe or provide references. For full board, unfunded studies describe sample size determination and power analysis. If none, please justify.

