Changes in blood pressure, heart rate, stroke volume, and vasopressor dose will be studied with paired t-tests. Based on prior studies of patients with sepsis, short-term variability of systolic blood pressure is about  $6\% \pm 4\%$  (Tavernier 1998, Michard 2000) after patients have received volume expansion. Taking this difference in blood pressure as the minimum clinically important difference, a sample size of about 12-15 patients will be needed for a power of 0.9 and  $\alpha$  of 0.05 to show a 6mm or greater difference in blood pressure.

Please save frequently

e) State if deception (including incomplete disclosure of study purpose/procedures) will be used. If so, describe the nature of the deception and provide a rationale for its use. Also, describe debriefing procedures or justify a waiver of the requirement to debrief. NOTE: for studies using deception, an alteration of consent must be justified in the Informed Consent section of the protocol (#13) and the debriefing script/statement must be uploaded in the Attachments section

Protocol Title: Hemodynamic effects of blood flow variation in continuous renal replacement therapy

---

(#16). See IRB Deception Guidelines.

f) Is there an accepted standard of care and/or standard practice at SLU for the condition/disease/situation being studied? This information will assist in comparing the risk/benefit ratio of study procedures relevant to usual care that would be received outside of the research context. \*?HELP?\* Y

If yes, please describe the standard of care and standard practice at SLU for the condition/disease/situation being studied.

All portions of the experimental protocol are within standards of care. The NxStage Cartridge Express device is approved for blood flows from 50-600 ml per minute. We will be studying blood flows within this range. The usual blood flow rate prescribed at Saint Louis University Hospital is 200-300 ml per minute. The dialysate flow rate and composition will be determined by standards of care and the judgment of the nephrology consult attending physician, and will not be altered in the study.

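### The only hypothesis, a systolic pressure change under 6 mmHg, has no test or decision rule: section 3d plans paired t-tests and a sample size aimed at the opposite conclusion

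*Combined protocol and SAP*

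**What the plan says.** Section 2b states one hypothesis: within the blood flow range in use and at fixed dialysate flow, the effect on the patient's haemodynamics "will be clinically insignificant, as defined as a change in systolic blood pressure of less than 6mm mercury". It refers the reader to section 3d. The specific aim that follows is one of estimation: "The goal of the study is to estimate the change hemodynamic parameters that occurs (if any) when blood flow is varied" over that range.

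Section 3d gives the whole analysis in one sentence: "Changes in blood pressure, heart rate, stroke volume, and vasopressor dose will be studied with paired t-tests". It then takes 6 as the minimum clinically important difference and says that "a sample size of about 12-15 patients will be needed for a power of 0.9" and an alpha of 0.05 "to show a 6mm or greater difference in blood pressure".

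Section 3b describes three 10-minute periods at 150, 350 and 150 ml/min with readings every minute. It explains the return to low flow: "Repeating measurements at low blood flow will permit estimation of time-dependent effects". Section 3d does not say which periods the paired test compares.

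**The concern.** The hypothesis is that a change lies inside a limit. An ordinary paired t-test asks whether the change differs from zero, and the sample size is set for detecting a change of 6 mmHg or more. Neither addresses whether the change is below 6 mmHg, and no interval or rule fills the gap.

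The plan can therefore mislead in two directions. A non-significant result may be read as confirming the hypothesis although the data still allow a change above 6 mmHg. A significant result may be read as refuting it although the change is smaller than 6 mmHg. The first error matters more here, because section 1 gives as motive the question whether blood flow can safely be raised in patients who cannot be anticoagulated.

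Three smaller gaps make the problem worse. An estimation aim is stated without an interval, the systolic contrast among the three periods is not named, and no SD of the within-patient change is given.

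**Working it through.** **Inputs.** From 2b and 3d: limit 6 mmHg, n = 12 to 15, power 0.9, alpha 0.05. Assumed: alpha is two-sided (not stated), the t-test null is zero (not written, but it is the default), and the limit is ±6 mmHg (no direction is given). The SD of the paired change, σ, is not stated; the 6% ± 4% variability in 3d is not an SD of a paired change in mmHg.

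**Step 1: the plan's own figure.** Paired t-test power is P(|T| > t(0.975, n−1)), where T is noncentral t with n−1 degrees of freedom and noncentrality δ√n/σ. At δ = 6, 90% power needs:
- n = 12: σ = 5.83
- n = 15: σ = 6.66

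So 12 to 15 patients is reproduced only if σ is about 5.8 to 6.7 mmHg. With one-sided alpha the range would be 6.65 to 7.54.

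**Step 2: what the t-test does on either side of the limit.**

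| | n = 12, σ 5.8 / 6.7 | n = 15, σ 5.8 / 6.7 | σ = 10, n = 12 / 15 |
|---|---|---|---|
| True change 6: non-significant | 9.7% / 19.4% | 3.9% / 10.3% | 52.5% / 42.0% |
| True change 3: significant | 37.3% / 29.4% | 46.2% / 36.5% | 15.8% / 19.2% |

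**Step 3: what a result just short of significance still allows.** The largest non-significant mean is t(0.975, n−1)·s/√n. Its upper 90% limit adds t(0.95, n−1)·s/√n.
- n = 12, s = 5.8: 2.201 × 5.8/√12 = 3.69; plus 1.796 × 5.8/√12 = 3.01; limit about 6.7.
- n = 12, s = 6.7: 4.26 + 3.47 = 7.73.
- n = 15, s = 5.8: 2.145 × 5.8/√15 = 3.21; plus 1.761 × 5.8/√15 = 2.64; limit 5.85.
- n = 15, s = 6.7: 3.71 + 3.05 = 6.76.

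Except at the most favourable corner, such a result does not exclude 6 mmHg.

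**Step 4: a test that fits the hypothesis.** Two one-sided tests at 5% each are the same as requiring the 90% interval, mean ± t(0.95, n−1)·s/√n, to lie within ±6. Power, integrated over the sampling distribution of s:

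| σ | True change | n = 12 | n = 15 | n for 90% power |
|---|---|---|---|---|
| 5.8 | 0 | 91% | 97% | 12 |
| 6 | 0 | 89% | 96% | 13 |
| 6 | 2 | 69% | 79% | 21 |
| 6.7 | 0 | 79% | 90% | 15 |
| 8 | 0 | 57% | 74% | 21 |
| 10 | 0 | 27% | 43% | 32 |

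At a true change of 6 mmHg this rule wrongly claims insignificance at most 5% of the time, whatever σ is. Reading non-significance as support has no such ceiling, as the last column of the Step 2 table shows.

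**The case against.** The strongest reply has four parts.

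- **A threshold exists.** Section 2b gives 6 mmHg, and a paired t analysis yields a mean and standard error from which an interval could be formed. That is true. What is missing is a commitment to compare the interval with 6 mmHg; until that is written, no stated analysis uses the threshold.
- **The percentages combine SDs and sample sizes.** The SD of 5.83 belongs to n = 12 and 6.66 to n = 15. On those matched pairs a true 6 mmHg change is missed in 10% of trials, which is simply the planned type II error; a true 3 mmHg change is significant in 37%; and the limit in Step 3 is about 6.7 mmHg. This is fair: the 19% and 7.7 mmHg figures need an SD slightly above what 12 patients were sized for. Since the plan states no SD, the range is still the right thing to show.
- **Step 3 describes a borderline result.** In simulated matched pairs, about 7% of non-significant results have a 90% interval reaching beyond ±6 when the true change is 0, and about 30% when it is 3 mmHg. So misreading is not the usual outcome if the implied SD is right. At an assumed SD of 10 mmHg and true change 0, the share is 54–71%.
- **The sample size may be adequate.** At the implied SD and a true change of 0, the equivalence test needs the same 12 to 15 patients. That is accepted; the sample size is not shown to be wrong.

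The null of zero and the two-sided alpha are inferences, as marked above. None of these points supplies a rule linking the planned analysis to the hypothesis.

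**Conclusion.** The concern holds and should be fixed before analysis. The study's single hypothesis cannot be confirmed or refuted by anything section 3d specifies, and its power statement is directed at showing a difference rather than excluding one. This mismatch is visible in the text and does not depend on any assumed SD.

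The size of the resulting error does depend on the SD. At the 5.8 to 6.7 mmHg implied by the stated sample size, treating the t-test as the answer misses a true 6 mmHg change in 4–19% of trials and flags a true 3 mmHg change in 29–46%. At an SD of 10 mmHg, an assumption used only for sensitivity, 42–53% of true 6 mmHg changes would be missed. These figures assume normally distributed paired changes, two-sided alpha of 0.05 and a limit of ±6 mmHg.

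**What to change.** Add to section 3d:

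1. **One systolic contrast.** For example, each patient's mean systolic pressure in period 2 minus the average of the means in periods 1 and 3, which uses the repeated low-flow period for the purpose 3b gives it. Other contrasts are defensible; one must be named.
2. **A decision rule.** Conclude that the effect is clinically insignificant only if the whole 90% confidence interval for the mean contrast lies within −6 to +6 mmHg (two one-sided tests at 5% each).
3. **Estimates with confidence intervals** for all haemodynamic variables, to serve the estimation aim in 2b.
4. **The assumed SD of the contrast, with power for this test** at 12 to 15 patients, as in Step 4. State the unit of the limit as well: 3d moves from 6% to 6 mm, which agree only at a systolic pressure of 100 mmHg (6/0.06).

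The cost is a few sentences, with no added patients, readings or procedures proposed. The drawback is that the stated power may look worse. It falls below 90% if the SD exceeds about 6 mmHg or the true change is not zero; at a true change of 3 mmHg it is only about 51% on the matched SD and sample size pairs. If the SD is thought to be nearer 8 or 10 mmHg, 90% power at zero change needs 21 or 32 patients, and the sponsor should either accept lower power openly or revisit the sample size.

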**Please save frequently**

**c) Describe the study design (e.g., single/double blind, parallel, crossover, control, experimental, observational, etc.). If the study is investigator-initiated, a timeline for individual subject recruitment, follow-up, and analysis for the study is required. Also, indicate if the subjects will be randomized.**

Prospective, cross-over, non-randomized study.

Timeline:

Recruitment: 18 months

Follow-up: subjects will be monitored for the 30 minutes during study protocol and for an additional 10 minutes. As this is a physiological study using an FDA-approved device being used in an FDA-approved manner after the clinical decision has already been made to institute therapy, long-term followup will not be required.

Analysis: Data analysis and publication will take one year after study is completed.

**d) If subjects will be given placebo, please justify placebo use. \*?HELP?\***

NA

### 3. Study Procedures

**a) N** Is this project a multicenter study (i.e., same project is conducted elsewhere by a different investigator) OR does this study involve conduct of research at multiple sites?  
Is SLU acting as a coordinating center for other sites OR is the SLU PI a direct recipient of a federal grant for this research? If yes, complete and attach the Supplemental

**Protocol Title:** Hemodynamic effects of blood flow variation in continuous renal replacement therapy

---

Application for Coordinating Center Activities.

Will the SLU site be participating in all parts/procedures/arms of the study?

If No, explain what SLU will NOT participate in:

**Please save frequently**

Page numbers from a sponsor's protocol/grant may be referenced in 3b, 3c, and 3d.

b) Describe all the procedures, from screening through end-of-study, that the human subject must undergo in the research project, including study visits, drug treatments, randomization and the procedures that are part of standard of care. Specify which procedures are for research and which are standard of care. Please note: The box below is for text only. If you would like to add tables, charts, etc., attach those files in the Attachment section (#16).

Screening: subjects on CRRT who are on the medical ICU service will be screened for inclusion and exclusion criteria.

Informed consent: Consent will be obtained from patients or a health care proxy (in cases where patient does not have capacity to give consent) in a private room. The consent process is detailed in section 8d of this submission and attached consent form.

The study procedure and enrollment of patients receiving CRRT through the division of Nephrology at Saint Louis University has been approved by division chief [name]. [name], director of the medical ICU, is a coinvestigator and has approved the protocol and enrollment of eligible patients on the MICU service. When a patient is enrolled in the study, [name], a coinvestigator and faculty member with the division of Nephrology, will ensure that CRRT orders reflect the study protocol. The ICU physician conducting the study protocol will ensure that if the patient is prescribed vasopressors, titration orders are modified to reflect the study protocol; vasopressor dose will remain constant as long as blood pressure remains within the protocol-specified parameters, but may be titrated if patients develop any pre-specified safety endpoints, adverse reactions or at physician discretion if clinically indicated. If a patient is enrolled, this will be communicated to the physicians on nephrology consult and the medical intensive care unit teams caring for the patient. All study procedures are consistent with FDA-approved uses of the dialysis device and are within established standards of care.

Procedure: An attending or fellow physician who is a member of the investigator team will supervise the entire protocol at the bedside. An ICU nurse will be present during the protocol. The study physician will ensure that patient's MAP is  $\geq 65$  mm Hg prior to initiating protocol. The study protocol is divided into three periods, each lasting 10 minutes. During all three periods, dialysate flow rate will be as prescribed by the nephrology consult attending physician, and fluid removal will be set to minimal.

The pre-specified protocol BFR rates of 150 and 350 ml/min were chosen because these are values at the lower and higher end of standard of care, respectively, and the range outside of which circuit lifespan observational studies suggest circuit lifespan may decrease (Dunn 2014). The protocol consists of two separate periods of BFR set to 150 in order to account for the influence of time on hemodynamics, separate from the influence of BFR. To clarify, if hemodynamics change from period 1 to period 2, it will not be clear if this is due to change in blood flow or changes over time. Repeating measurements at low blood flow will permit estimation of time-dependent effects. Large randomized trials involving the use of CRRT have used blood flows similar to those being studied in this protocol (Vinsonneau 2006, Palevsky 2008).

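### Section 3d analyses systolic pressure without regard to vasopressor titration, which can pull the result toward the hypothesised small change; the paired t-test on dose is a minor related weakness

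*Combined protocol and SAP*

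**What the plan says.** Section 3b (procedures) fixes the dose during the protocol, with exceptions: "vasopressor dose will remain constant as long as blood pressure remains within the protocol-specified parameters, but may be titrated". The grounds are wide: the dose "may be titrated if patients develop any pre-specified safety endpoints, adverse reactions or at physician discretion if clinically indicated". Not every patient need be on a vasopressor, since the instruction reads "if the patient is prescribed vasopressors, titration orders are modified to reflect the study protocol".

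Section 3d gives the analysis in one sentence: "Changes in blood pressure, heart rate, stroke volume, and vasopressor dose will be studied with paired t-tests". It does not say whether readings after a titration are kept, dropped or adjusted for, whether patients without vasopressors enter the dose test, or whether tests are one- or two-sided. The sample size rests on blood pressure alone: "a sample size of about 12-15 patients will be needed for a power of 0.9".

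Two other statements bear on this. Section 2b sets the hypothesis, a clinically insignificant effect, on systolic pressure, "as defined as a change in systolic blood pressure of less than 6mm mercury", and describes the aim as estimation: "The goal of the study is to estimate the change hemodynamic parameters that occurs (if any) when blood flow is varied". Section 3b explains the return to low flow in period 3: "Repeating measurements at low blood flow will permit estimation of time-dependent effects".

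**The concern.** Titration responds to the outcome. If pressure falls after flow is raised and the dose is increased in response, the later readings carry the drug effect as well as the flow effect. In a comparison of period 1 with period 2 this moves the observed change toward zero, which is the result the study hypothesises. The increase may then persist into period 3, where it would be taken for a time effect.

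A lesser issue concerns dose as an outcome. Because dose moves only by exception, most within-patient differences may be exactly zero. A t-test on such data says little, and a non-significant result could be mistaken for evidence of no haemodynamic effect.

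**Working it through.** **1. The plan's sample size.** Section 3d gives a 6 mm Hg difference, power 0.9 and alpha 0.05, but no standard deviation (SD) of the paired difference in mm Hg. With an assumed SD of 6 mm Hg, the normal approximation n = (SD × (1.960 + 1.282) / 6)² gives 10.5, so 11; the two-sided t calculation gives 13. Working back, 12 to 15 patients corresponds to an SD of about 5.8 to 6.7 mm Hg. The figure is plausible but cannot be confirmed. It makes no allowance for titration.

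**2. Effect of a titration on systolic pressure.** Section 3b gives ten readings per period. Everything else here is assumed. Take two patients whose period 2 readings are expressed as change from their period 1 mean, with titration adding 10 mm Hg to each later reading.

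| Period 2 pattern without titration | Untreated mean | All readings | Post-titration readings excluded |
|---|---|---|---|
| A: single dip of 10 at minute 5, otherwise 0; titrated after minute 5 | -10/10 = -1 | (-10 + 5 × 10)/10 = +4 | -10/5 = -2 |
| B: 0 for two minutes, then -10 throughout; titrated after minute 3 | 8 × (-10)/10 = -8 | -10/10 = -1 | -10/3 = -3.3 |

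- Keeping all readings raises the patient's mean change by 5 mm Hg (A) or 7 mm Hg (B), which hides the fall in both.
- Excluding later readings exaggerates the fall in A, because the retained readings end at the triggering low. In B it understates the fall, because much of what is retained precedes it.
- If the added 10 mm Hg persists, period 3 minus period 1 is 10 mm Hg too high in either patient.
- One such patient moves the study mean for period 1 versus 2 by 5/15 = 0.33 to 7/12 = 0.58 mm Hg; three move it by 15/15 = 1.0 to 21/12 = 1.75 mm Hg.

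A harsher illustration by simulation assumed a true mean fall of 6 mm Hg and an SD giving 90% power, with titration returning the largest fallers wholly to no change. With two such patients the observed mean fall was about 3.7 (n = 12) to 3.9 (n = 15) mm Hg and power about 0.71 to 0.72. With three it was about 2.8 to 3.1 mm Hg, and power 0.57 to 0.61.

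**3. The t-test on dose.** Suppose k of n patients have a dose change and the rest enter as zero. For fixed k, t is largest when all k changes are equal and in one direction, giving t = √(k(n − 1)/(n − k)) on n − 1 degrees of freedom. For k = 3 this is √(3 × 11/9) = 1.915 at n = 12 and √(3 × 14/12) = 1.871 at n = 15.

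| k titrated | smallest two-sided p, n = 12 | smallest two-sided p, n = 15 |
|---|---|---|
| 0 | undefined | undefined |
| 1 | 0.339 | 0.334 |
| 2 | 0.166 | 0.164 |
| 3 | 0.0819 | 0.0824 |
| 4 | 0.0388 | 0.0406 |

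- One-sided, k = 3 can reach 0.041 at either n.
- If only patients on vasopressors enter (assumed 5, 8 or 10), k = 3 gives at best 0.071, 0.080 or 0.081 two-sided.
- Another test would not help: the exact sign or Wilcoxon two-sided p cannot go below 2 × 0.5^k, which is 0.25, 0.125, 0.0625 and 0.031 for k = 3 to 6.
- The chance of four or more titrations among 12 to 15 patients is 0.026 to 0.056 at an assumed 10% rate per patient, 0.21 to 0.35 at 20%, and 0.51 to 0.70 at 30%.

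**4. What counts would show.** With no titrations the exact 95% upper limit is 1 − 0.025^(1/n): 22% for 0 of 15, 26% for 0 of 12, 37% for 0 of 8. For 3 of 15 (20%) the exact limits are 4% and 48%.

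**The case against.** The design already limits titration: the dose is held, mean arterial pressure must be at least 65 mm Hg at the start, fluid removal is minimal, flow is changed in steps, and each period is short. The supplied text ends in section 3; a later section may end the procedure at a safety endpoint, leaving fewer post-titration readings. The all-readings analysis also answers a legitimate question, namely what happens when titration is allowed. All this stands, and it is why no size can be claimed. None of it tells the analyst what to do with readings taken after a titration.

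On dose, the objection is stronger. Dose is one of four listed variables, the hypothesis and sample size rest on blood pressure, and the plan nowhere says a non-significant dose result would be read as no effect. The discretion clause is broad, so titrations need not be rare. The limit of about 0.08 requires a two-sided test, zeros for the untitrated and at most three titrations; it does not apply if every patient in the test is titrated. The weakness comes from sparse data and is not peculiar to the t-test. This reduces the dose part to a reporting point.

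A reader might also infer that dropping post-titration readings gives the unbiased answer, or that it always errs toward no effect. Neither holds: the direction depends on the contrast and on when the titration occurs.

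**Conclusion.** The concern holds at modest weight, with systolic pressure as the lead. Section 3d pools readings whether or not the dose has changed. For period 1 versus 2, an increase given for low pressure biases the observed change toward the hypothesised result; a period 2 increase that persists also contaminates the period 3 estimate of time effects. The size is unknown, and the figures in mm Hg above are illustrations on assumed inputs.

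A reader might infer that the systolic result is bound to be masked, or that the dose test cannot reach significance. The documents support neither: they give no titration rate and no share of patients on vasopressors, and four changes in the same direction can reach p of about 0.04. The dose part is minor and conditional on few titrations.

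**What to change.** Amend section 3d only, leaving the titration rule unchanged.

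1. Keep the paired systolic analysis on all readings. State that titration for low pressure can bias it toward no change, so a result under 6 mm Hg must be read beside the titration counts.
2. Add a sensitivity analysis that excludes systolic readings taken after a titration, with the same exclusion for heart rate and stroke volume. State its bias by contrast. For period 1 versus 2, a patient titrated in period 2 stays in and the retained readings end at the low value, so the fall may be exaggerated (though an early titration in a sustained fall can do the reverse). For contrasts with period 3, or after a period 1 titration, the patient drops out, which may bias toward no effect. Report how many patients are left without a usable pair.
3. Replace the dose t-test with the number and proportion of patients with any increase and, separately, any decrease in each period, among those on vasopressors, with exact 95% confidence intervals. List the size and timing of each change. State that a non-significant dose result is not evidence of no effect.

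The cost is a few lines of text and reporting; dose and pressure are already recorded each minute. The sensitivity analysis has fewer readings: a patient titrated in period 2 loses all 10 period 3 readings, and one titrated in period 1 loses the 20 readings of periods 2 and 3. It therefore supplements the all-readings analysis and does not replace it.
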